5.0 STUDY DEVICES

The materials presented in Table 4 are the devices required for the supervised and remote evaluation periods. In addition to the investigational device, a Heart Rate Reference Device and a Respiration Reference Device will be used in this study, and will be applied to the subject as shown in Figure 2. Identification as well as traceability for each investigational and reference device at the study site will be maintained by serial number.

The Actiheart (K052489, CamNtech Inc., Cambridge, UK), used here as the Heart Rate Reference device, is a commercially-available, FDA-cleared, chest-worn monitoring device that records heart rate, Inter-Beat-Interval (IBI), and physical activity. It is designed for calculating and measuring heart rate and Energy Expenditure in free living. The Actiheart has two clips which attach directly to standard ECG electrodes. Usually one electrode is adhered at V1 or V2 (4th intercostal) and the second electrode is placed approximately 10cm away on the left side at V4 or V5, although this placement can be adjusted to be more comfortable for the subject. The number of R-waves detected is recorded, and an internal accelerometer senses the frequency and intensity of the subject's torso movements.

The Capnostream Portable Respiratory Monitor (K150272, Medtronic Inc., Dublin, IE) used here as the Respiration Reference device, is a commercially-available, FDA-approved, bedside, combined capnography/pulse oximetry monitor, capable of providing a complete picture of oxygenation and ventilation by monitoring a subject's:

[figure not shown]
- End tidal carbon dioxide (etCO₂) - level of carbon dioxide in exhaled breath.
- Respiratory rate (RR).
- Fractional inspired carbon dioxide (FiCO₂) - level of carbon dioxide present during inhalation.
- Oxygen saturation (SpO₂).
- Pulse rate (PR).

It is intended to provide professionally trained health care providers the continuous, non-invasive measurement and monitoring of carbon dioxide concentration of the expired and inspired breath and respiration rate, and for the continuous non-invasive monitoring of functional oxygen saturation of arterial hemoglobin (SpO₂ and pulse rate).

Additionally, a commercially-available manual “tally” counter will be used for counting steps.

Table 4: Devices for Study Activities

| Materials | Purpose | Supervised | Remote |
|--|---|------------|--------|
| MC10 BioStamp nPoint System | | | |
| Sensors | Investigational device | X | X |
| Link Hub | Investigational device | X | X |
| Adhesives | Investigational device | X | X |
| Adhesive Applicator | Investigational device | X | X |
| Mobile Phone with Link App | Investigational device | X | X |
| Actiheart (CamNtech Inc.) with electrodes | Reference device: Heart Rate (HR), Heart Rate Variability (HRV) | X | X |
| Capnostream 35 Portable Respiratory Monitor (Medtronic Inc.) with nasal cannula | Reference device: Respiration Rate | X | - |
| Manual step counter | Reference device: Step Counting | X | - |

| | |
|---|------------------------------|
| ■ | BioStamp nPoint Sensor |
| ■ | Heart Rate Reference Device |
| ■ | Respiration Reference Device |

Figure 2: Anatomical Locations for Investigational and Reference Devices

6.0 STUDY DESIGN

The study design is a non-significant risk, open-label, prospective non-randomized clinical investigation designed to validate the accuracy of the various physiological parameters that the MC10 Sensors acquire and the system processes, and to validate the performance of the Sensor skin adhesive. The study will be conducted at a single site in the United States.

[figure not shown]

Figure 3: Study Design Flow Chart

6.1 Study Duration

One supervised session of approximately four hours, with observation periods throughout and two night-time sleep periods; thus a total evaluation duration of approximately 48 hours.

At least one safety and tolerability follow-up call will occur within three to five days post-sensor removal.

6.2 Schedule of Events

The evaluation period includes (refer to Section 4.1) clinician observed supervised testing. Subjects will wear a total of four BioStamp nPoint Sensors for this study; chest, thigh, shank, and forearm, and the BioStamp nPoint system will be configured, using only the chest and thigh Sensors, to measure and compute algorithm outputs.

In addition to the algorithm determinate Sensor locations, the shank and forearm Sensors (no sensor data will be collected) will be utilized in combination with the chest and thigh locations to validate the Sensor adhesion performance. The study is designed to capture supervised, observed measurements, as well as two nights of sleep in in clinic supervised setting.

Table 5: Schedule of Events

| Activities | Visit Day | Screening Period | Evaluation Period | | | | Safety Follow-Up |
|---|--------------|---------------------|-------------------|------------------|------------------|------------------|---------------------|
| | | 1 | Clinic 1 or 2 | Clinic 1 or 2 | Clinic 2 or 3 | Clinic 2 or 3 | Telephone |
| | | -60 to 0 | 0 | 1 | 1 | 2 | 3-5 |
| Screening & Enrollment Activities | | | | | | | |
| Informed Consent | | X | | | | | |
| Screening survey (demographics, medical history, etc.) | | X | | | | | |
| Baseline assessment (weight, Fitzpatrick, medical history, location irritation) | | X | X | | | | |
| Urine pregnancy and drug screen | | X | X | | | | |
| Sensor Application | | | | | | | |
| Application of Functional MC10 Sensors by Clinician | | | X | | | | |
| Application of Non-functional MC10 Sensors by Clinician | | | X | | | | |
| Adhesion application assessment | | | X | X | | | |
| Application of Functional MC10 Sensors by Subject | | | | X | | | |
| Application of Heart Rate Reference Device by clinician | | | X | | | | |
| Application of Respiration Reference Device for Sleep Respiration by clinician | | | X | | X | | |
| Prescribed Activities (Supervised) | | | | | | | |
| Activity Classification Activities | | | X | | | | |
| Heart Rate Activities | | | X | | | | |
| Subject training | | | | X | | | |
| Overnight sleep | | | X | | X | | |
| Prescribed Activities (Remote) | | | | | | | |
| | | | | X | | | |
| Time of Removal Assessments (MC10, Heart Rate Reference Device) | | | | | | | |
| Adhesion assessment | | | | X | | X | |
| Removal pain assessment | | | | X | | X | |
| Skin irritation assessment | | | | X | | X | |
| Sensor Removal | | | | | | | |
| Removal of Respiration Reference Device for Sleep Respiration by clinician | | | | X | | X | |
| Removal of MC10 Sensors by clinician | | | | X | | | |
| Clean MC10 Sensors by clinician | | | | X | | | |
| Removal of MC10 Sensors by Subject | | | | | | X | |
| Clean MC10 Sensors by Subject | | | | | | X | |
| Removal of Heart Rate Reference Device by clinician | | | | | | X | |
| Usability Survey | | | | X | | X | |
| Data Transfer | | | | | | | |
| MC10 Sensor data transfer | | | | X | | X | |
| Respiration Reference Device data transfer | | | | X | | X | |
| Heart Rate Reference Device data transfer | | | | | | X | |
| Return sensors to investigators | | | | | | X | |
| Safety follow-up call | | | | | | | X |
| Recording of adverse events | | | X | X | X | X | X |

7.0 STUDY POPULATION

Subjects must meet all inclusion criteria for enrollment in the clinical study and have no exclusion criteria. Reasons for screening failure(s) will be documented.

7.1 Number of Subjects

Minimally, twenty-five (25) healthy subjects (defined as people who do not have the condition or related conditions or symptoms being studied to participate in that study; see also “Accepts Healthy Volunteers” on ClinicalTrials.gov) minimally will be enrolled in the study.

7.1.1 Inclusion Criteria

Subjects must meet all of the following criteria to be eligible for participation in the study:

1. Male or female volunteers, at least 18 years of age at the time of screening visit;
2. Fluent in English;
3. The subject is willing and physically able to comply with the protocol specified evaluations;
4. Subject is willing and is cognitively able to sign informed consent

7.1.2 Exclusion Criteria

Subjects must be excluded from participation in this study if any of the following criteria are met:

1. Pregnancy;
2. Positive urine drug screen
3. History of active (clinically significant) skin disorders;
4. History of allergic response to silicones or adhesives;
5. Subjects with electronic implants of any kind (e.g. pacemaker)
6. History of sleep disorders or self-reported insomnia or other sleep conditions;
7. Broken, damaged or irritated skin or rashes near the sensor application sites;
8. Subjects that are MC10 employees or shareholders, or a spouse or child of an MC10 employee or shareholder;
9. Subjects who are physically or cognitively unable to normally perform activities of daily living, assessed at the discretion of the investigator.

8.0 STUDY PROCEDURES & ASSESSMENTS

The visit schedule, study procedures, and assessments are presented in the Study Design Flow Chart (Figure 3) and the Schedule of Events (Table 5). Site personnel will be instructed via training conducted by MC10 of the investigational device and reference devices protocol specific operation and use and will be documented and approved by MC10 via a verification form.

8.1 Device and System Configuration

Prior to first subject enrollment, for the investigational device, MC10 will design, via the Web Portal, the study activities associated with the BioStamp nPoint system, including appropriate annotation prompts required for execution.

The reference devices and associated software will be configured as necessary to maintain subject traceability and facilitate subsequent data management and analysis. Study site staff will be trained on the proper configuration, application, and use of the reference devices that are presented in Section 5.0 per their associated Instructions for Use as they pertain to the metrics required to fulfill the study objectives.

8.2 Subject Identification

Each subject will be assigned a unique subject number. Subject numbers will not be reassigned or reused for any reason. Only their assigned subject number, initials, and date of birth should identify subjects to the Sponsor. The investigator must maintain a list of potential subjects and enrolled subjects using the Subject Screening/Enrollment Log. At a minimum, this log is faxed (or emailed) to the Sponsor each week. Site will also maintain a Subject ID List in the PI's records ensuring that subjects may be identified in case of product recalls or safety issues.

Any potential subjects who are pre-screened can be added to the log by recording their screening number and initials only. Those who sign the ICF will be assigned a five-digit sequential number. The first two digits will represent the site number (i.e., 01) and the remaining three digits are a sequential patient number (i.e., 001, 002, 003, etc.). Therefore, the fourth subject screened at site number one will be Subject #01004.

8.3 Recruitment

Participants will be recruited via an established database at the clinical site, use of IRB approved flyers and posting on the clinical site website. The completely voluntary nature of participation will be underscored.

8.4 Subject Eligibility, Pre-Screening and Exclusions

Subjects will be asked to participate in this study and will be screened for study eligibility. Each subject will receive an anonymized subject identification number at time of screening that will serve as the subject's identifier throughout the study. A Screening/Enrollment Log will be maintained by the study site, in order to maintain a cumulative tracking of all screened subjects.

8.5 Written Informed Consent

Subjects who pass initial pre-screening will be asked to sign the study-specific Informed Consent form before any study-specific tests or procedures are performed. A member of the research team will inform the potential subject of the elements of the clinical study including, risks, potential benefits and required procedures prior to obtaining the potential subject's informed consent.

8.6 Screening and Baseline (Day 0) Evaluation

The following evaluations are required at the time of subject screening/baseline:

1. Urine pregnancy test and drug screen;
2. Medical History & Current Status – skin disorders;
3. Medical History & Current Status – allergies;
4. Medical History & Current Status – electronic implants;
5. Medical History & Current Status – insomnia/sleep conditions;
6. Evaluation of application sites for broken, damaged, or irritated skin or rashes;
7. MC10 affiliation survey/question
8. Demographics Information: Age, Gender, Height, Weight, Fitzpatrick skin type.

Source documents related to screening activities will be filled out for all screened subjects.

8.7 Subject Enrollment

Subjects who meet all inclusion and none of the exclusion criteria will be considered eligible for enrollment. Subjects will be considered enrolled at Visit 1 prior to application of study devices and measurement capability of the device on the subject has been verified. If the subject does not meet the eligibility criteria at any time before enrollment then the subject will be considered a screen failure. Once enrolled, a subject may only exit the study as a withdrawal (not a screen failure). The reason

for withdrawal will be documented by the investigator on the Study Termination CRF and early termination procedures will be completed for all withdrawn subjects. All records of enrolled but withdrawn subjects will be retained as part of the study.

8.8 Study Assessments – In Clinic – Visit 1 (Supervised)

During the supervised evaluation period, subjects will arrive at the study clinic on Day 0. After admission to the clinic, but before the start of the evaluation period, a skin inspection of planned sensor application sites will be conducted.

The clinical site staff will provision Sensors, a Link Hub, and a Link App phone to the subject using the Link App. They will then apply four Sensors and reference device sensors to the subject. Two of these Sensors will be applied following instructions on the Link App; the other two are for assessing adhesion only, and will be applied following written instructions.

Site staff will then initiate and monitor the prescribed activities for the supervised portion of the study. The prescribed activities consist of general tasks: sitting, standing, lying down, leaning, walking, and biking. The site staff will instruct the subject throughout the evaluation.

For each of the prescribed activities, the site staff will start an annotation in the MC10 Link App to indicate that the subject is starting to perform an activity and will stop the annotation after a specific period of time when the subject has completed the activity. Each annotation will be tagged with a letter and a number. The letter and number used for the annotation of each activity performed will be noted on the CRF. The following activities will be conducted as prescribed in sections 8.8.2 - 8.8.7.

8.8.1 Application of the Heart Rate Reference Device

The Heart Rate Reference Device will be applied as described in Section 5.0, following the manufacturer’s IFU, 30 minutes prior to the start of study activities to allow for sensor to body continuity. Heart rate will be monitored throughout the study including during the activities in Table 7 and Table 8.

8.8.2 BioStamp nPoint Sensor Application

The clinician will apply sensors (turned off, no signal data) to the shank and forearm, and functional sensors to the chest, aligned to 60 degrees from the transverse plane with the battery end pointed upwards (left nipple to right shoulder), and thigh, aligned vertically on the central thigh with the battery end pointed upwards, as prescribed by the BioStamp nPoint system IFU. MC10 Sensor adhesion will be assessed (refer to Table 3). The activities in Table 6 will be conducted and annotated following the guided prompts provided by the Link App.

Table 6: Application Activities

| Item | Activity | Description | Time | Repetitions |
|------|---------------------|--|------|-------------|
| 1 | Posture Calibration | Subject stands still in an upright vertical position | 10 s | 1 |

8.8.3 Activity Classification

The activities in Table 7 will be conducted as prescribed, in a variable order, and will be annotated by the clinician marking the start and stop times for each activity using the Link App. The particular activity performed for a given annotation will be noted on the CRF. This set of activities will be performed 5 times in a random order each time, as listed in the Repetitions column of Table 7.

Table 7: Activity Classification Activities

| Item | Activity | Description | Time | Repetitions | Metric |
|------|-------------------------|--|-------|-------------|--|
| 1 | Standing Classification | Instruct the subject to stand upright. Once the subject is standing upright, start the activity. | 1 min | 5 | ADL Classifier – Standing HR/HRV – Resting |
| 2 | Sitting Classification | Instruct the subject to sit in a chair. Once the subject is sitting, start the activity. | 1 min | 5 | ADL Classifier – Sitting HR/HRV – Resting |
| 3 | Lying Classification | Instruct the subject to lie supine. Once the subject is lying in a supine position, start the activity. | 1 min | 5 | ADL Lying HR/HRV – Resting |
| 4 | Standing Upright | Instruct the subject to stand against the marked wall, with their right side facing the wall. Instruct the subject to stand upright. Once the subject is in position, start the activity. | 1 min | 5 | Posture HR/HRV – Resting |
| 5 | Standing Leaning FRONT | Instruct the subject to stand against the marked wall, with their right side facing the wall. Instruct the subject to lean forward to the 30-degree mark. Once the subject is in position, start the activity. | 1 min | 5 | Posture HR/HRV – Resting |
| 6 | Standing Leaning BACK | Instruct the subject to stand against the marked wall, with their right side facing the wall. Instruct the subject to lean back to the 30-degree mark. Once the subject is in position, start the activity. | 1 min | 5 | Posture HR/HRV – Resting |
| 7 | Standing Leaning RIGHT | Instruct the subject to stand facing the marked wall. Instruct the subject to lean right to the 30-degree mark. Once the subject is in position, start the activity. | 1 min | 5 | Posture HR/HRV – Resting |
| 8 | Standing Leaning LEFT | Instruct the subject to stand facing the marked wall. Instruct the subject to lean left to the 30-degree mark. Once the subject is in position, start the activity. | 1 min | 5 | Posture HR/HRV – Resting |
| 9 | Sitting Upright | Instruct the subject to sit in a straight-backed chair. Instruct the subject to sit upright. Once the subject is in position, start the activity. | 1 min | 5 | Posture HR/HRV – Resting |
| 10 | Sitting Leaning FRONT | Instruct the subject to sit in a chair. Instruct the subject to lean forward to the 30-degree mark. Once the subject is in position, start the activity. | 1 min | 5 | Posture HR/HRV – Resting |
| 11 | Sitting Leaning BACK | Instruct the subject to sit in a chair. Instruct the subject to lean back to the 30-degree mark. Once the subject is in position, start the activity. | 1 min | 5 | Posture HR/HRV – Resting |
| 12 | Sitting Leaning RIGHT | Instruct the subject to sit in a chair. Instruct the subject to lean right to the 30-degree mark. Once the subject is in position, start the activity. | 1 min | 5 | Posture HR/HRV – Resting |
| 13 | Sitting Leaning LEFT | Instruct the subject to sit in a chair. Instruct the subject to lean left to the 30-degree mark. Once the subject is in position, start the activity. | 1 min | 5 | Posture HR/HRV – Resting |
| 14 | Lying SUPINE | Instruct the subject to lie on their back. Once the subject is in position, start the activity. | 1 min | 5 | Sleep posture HR/HRV – Resting |
| 15 | Lying PRONE | Instruct the subject to lie flat on their stomach. Once the subject is in position, start the activity. | 1 min | 5 | Sleep posture HR/HRV – Resting |
| 16 | Lying RIGHT | Instruct the subject to lie on their right side. Once the subject is in position, start the activity. | 1 min | 5 | Sleep posture HR/HRV – Resting |
| 17 | Lying LEFT | Instruct the subject to lie on their left side. Once the subject is in position, start the activity. | 1 min | 5 | Sleep posture HR/HRV – Resting |

| | | | | | |
|----|------------------------|---|-------|---|--|
| 18 | Walking | Instruct the subject to walk for 6 minutes. Once the subject starts walking, start the activity. Count total steps taken by the subject, both legs. Post-activity assessment: How many total steps did the subject take during the walking activity? | 6 min | 5 | ADL Classifier – Walking Pedometer HR/HRV – Moving |
| 19 | Walking Classification | Instruct the subject to walk on the treadmill at a constant, comfortable pace. Once the subject starts walking, start the activity. | 1 min | 5 | ADL Classifier – Walking |
| 20 | Other Classification | Instruct the subject to bike at a constant, comfortable, low-intensity pace. Once the subject starts biking, start the activity. | 8 min | 5 | ADL Classifier – Other HR/HRV – Moving |

8.8.1 Heart Rate Activities

The activities in Table 8 will be conducted as prescribed and will be annotated by the subject marking the start and stop times for each activity using the Link App. The clinician will train the subject on Link App operation and monitor subject performance to ensure that the activities are properly annotated.

Table 8: Heart Rate Activities

| Item | Activity | Description | Time (minimum) | Repetitions | Metric |
|------|----------|--|----------------|---------------------|------------------|
| 1 | Sitting | Sit comfortably in a chair | 22 min | At least 2, up to 4 | HR/HRV – Resting |
| 2 | Walking | Walk on a treadmill at a comfortable pace | 22 min | At least 2, up to 4 | HR/HRV – Moving |
| 3 | Biking | Bike on a recumbent bike at a comfortable pace | 22 min | At least 2, up to 4 | HR/HRV – Moving |

8.8.2 Application of the Respiration Reference Device

The Respiration Reference Device will be applied as prescribed in Section 5.0, following the manufacturer’s IFU, prior to the subject going to bed.

8.8.3 Night-Time Sleep Duration

When the subject goes to bed (lights out) and arises from bed (woken by site staff), the sleep onset time and wake time will be recorded by site staff on the CRF. Subjects will be observed throughout the night to annotate on the CRF any periods of wakefulness between these times.

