2.0 DEVICE DESCRIPTION

The BioStamp nPoint system is a wireless remote monitoring platform intended for use by healthcare professionals and researchers for the continuous collection of physiological data in home and healthcare settings. The system is designed principally for data collection during research studies although may be used wherever and whenever collection of the relevant data is needed.

Figure 1: Illustration of BioStamp nPoint Sensor

The BioStamp nPoint system centers on body-worn Wearable Sensor Patches (“Sensors”, “WSPs”) which can be worn in both in clinic (“supervised”) and remote (“unsupervised”) settings for up to 24 hours at a time, and can be worn repeatedly for multiple days. Study facilitators (either researchers or physicians) set up data collection studies using a web-based study configuration tool, called the Web Portal. For in-clinic uses, the BioStamp nPoint system includes an Investigator Tablet Application that study facilitators use to connect to and configure Sensors. When used at home, study subjects interact with the system through a Mobile Phone Application, the Link App. The Link Hub is used to charge and synchronize data from the Sensors. The BioStamp nPoint system includes an algorithm package that delivers processed metrics on general activity classification, heart rate, heart rate variability, posture, sleep, and respiration during sleep.

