4.0 STUDY ENDPOINTS

4.1 Effectiveness Endpoints

The effectiveness endpoints for this study are the various types of measurements made by the BioStamp nPoint system. All effectiveness endpoints to be statistically summarized will be collected using the BioStamp nPoint during in clinic supervised use. The effectiveness endpoints are as follows:

- Heart Rate (bpm)
- Heart Rate Variability (RMSSD³ (msec) and LF/HF Ratio⁴)
- Respiration (average respiration rate)
- Activity Classification (activities – sleep, standing, sitting, lying, walking and other)
- Activity Parameters - total step counts in a 6 minute walk test
- Sleep (sleep onset time (hours, minutes, and seconds), sleep wake time (hours, minutes, and seconds))
- Posture Classification (sleep posture, stationary posture standing, stationary posture sitting)

For each endpoint, the BioStamp nPoint measurements will be compared to a similar FDA-cleared measurement device, other measurement devices, or independent observer measurements. The FDA-cleared measurement devices used as comparators for this study are the Actiheart heart rate reference device and the Capnostream portable respiratory monitor.

Table 1 displays the comparator method for each endpoint category.

Table 1: Endpoint Variable Group and Measurement Comparator

| Index | Endpoint Variable Group | Measurement Comparator |
|-------|-------------------------|-----------------------------|
| 1 | Heart Rate | Actiheart Device |
| 2 | Heart Rate Variability | Actiheart Device |
| 3 | Respiration | Capnostream Device |
| 4 | Activity Classification | Independent Observer |
| 5 | Activity Parameters | Manual Step Counting Device |
| 6 | Sleep Parameters | Independent Observer |
| 7 | Posture | Independent Observer |

³ RMSSD: root-mean-square of successive difference of the time intervals between successive heartbeats.

⁴ LF/HF ratio: the ratio of power in the low-frequency (LF, 0.04-0.15 Hz) and high-frequency (HF, 0.15-0.4 Hz) bands of heart rate variability in the frequency domain.

Individual independent observers will receive training on the operation of all devices and execution of the study protocol before the enrollment of any subjects.

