For heart rate and heart rate variability, the values collected will be the one minute average heart rate, the one minute RMSSD and the five-minute LF/HF ratio from the BioStamp nPoint and the one minute average heart rate, RMSSD and five minute LF/HF ratio from the Actiheart device on each of six recording times for each subject. Two readings will be taken while the subject is at rest, two while exercising and two while lying down.

For respiration rate, the average sleep respiration rate values will be collected at one minute time intervals during two separate nights of sleep on each subject using both the BioStamp nPoint and the Capnostream while the subject is asleep.

For the activity classification variable, each subject will be presented with five tasks (standing, sitting, lying, walking and stationary bike riding) in varied order and the activity classification will be recorded by the BioStamp nPoint and by the independent observer. This procedure will be repeated five times for each subject.

For the exercise parameter number of steps taken, the number of steps taken by the subject during a 6 minute walk test will be recorded using both the BioStamp nPoint and a simple step counting device.

For the sleep parameters sleep onset time and wake time, the BioStamp nPoint values and independent observer values will be collected on each night at the study site.

Posture classification variables will be analyzed separately for each type of posture activity (sleep positions, stationary posture standing and stationary posture sitting). For a given posture activity, the posture classification will be recorded by the BioStamp nPoint and the independent observer for two repeats each of each ground-truth posture for each subject. Since sleep position and lying posture are identical, this variable will be assessed from awake subjects to ensure that all postures are represented. Each repeat will generate 5 independent observations of posture. The posture classifications for each posture classification variable are given in Table 2.

Table 2: Posture Variable and Classification

| Index | Posture Variable | Posture Classification |
|-------|-----------------------------|---|
| 1 | Sleep positions | Supine, prone, left side and right side |
| 2 | Stationary Posture Standing | Upright, lean left, lean right, lean back, lean forward |
| 3 | Stationary Posture Sitting | Upright, lean left, lean right, lean back, lean forward |

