8.10.1 Night-Time Sleep Duration

When the subject goes to bed (lights out) and arises from bed (woken by site staff) the sleep onset time and wake time will be recorded by site staff on the CRF. Subjects will be observed throughout the night to annotate on the CRF any periods of wakefulness between these times

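### The observer's sleep onset time is taken at lights out, so the reference is early by the sleep latency and the onset agreement figures are biased

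*Protocol*

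**What the plan says.** Two sections of the protocol set the rule, one per night. Section 8.8.3, Night-Time Sleep Duration (the number 8.8.3 is also used for Activity Classification), gives it for the first night: "goes to bed (lights out) and arises from bed (woken by site staff), the sleep onset time and wake time will be recorded". Clinic staff make the entry on the CRF. Section 8.10.1 repeats this for the second night: "goes to bed (lights out) and arises from bed (woken by site staff) the sleep onset time and wake time will be recorded". Both sections then provide for overnight observation: "Subjects will be observed throughout the night to annotate on the CRF any periods of wakefulness between these times".

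Section 4.1 defines the sleep endpoint as onset time and wake time, expressed as clock times to the second. Table 1 names the independent observer as comparator. The general rule is "For each endpoint, the BioStamp nPoint measurements will be compared to a similar FDA-cleared measurement device, other measurement devices, or independent observer measurements". Section 11.3 repeats the endpoint and comparator. Section 11.6.2 prescribes scatter plots, Bland-Altman plots, MAE and RMSE for continuous pairs.

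Elsewhere the protocol treats being asleep and lying down as different states. Section 4.1 lists the activity classes as "sleep, standing, sitting, lying, walking and other" and takes respiration pairs "using both the BioStamp nPoint and the Capnostream while the subject is asleep". Section 2.0 says only that the algorithm package "delivers processed metrics on general activity classification, heart rate, heart rate variability, posture, sleep, and respiration during sleep". It does not define what the device's sleep onset marks.

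**The concern.** The endpoint is called sleep onset time, but the reference value is the time the subject went to bed. Because wakefulness is annotated between the two recorded times, those times mark the limits of time in bed, not of sleep. On every night with a latency above zero, the reference is too early by that latency. It is never too late.

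This error lies in the reference and is systematic, so it passes straight into the agreement statistics. A Bland-Altman plot shows only the difference between device and reference and cannot say which of the two is off. The direction of the distortion depends on how the device behaves, which the protocol leaves open. An accurate onset detector looks worse than it is. A device that cannot tell quiet wakefulness in bed from sleep looks better than it is. Accuracy of the algorithm outputs is part of the primary objective (section 3.0), and these figures are the result for this endpoint.

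**Working it through.** The protocol states no sleep latency, no expected onset error and no acceptance limit, so it has no figure to reproduce. All latencies below are assumptions.

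**Inputs from the protocol.** Reference onset is lights out on both nights (8.8.3, 8.10.1). The measures are MAE, RMSE and Bland-Altman (11.6.2). There are 25 subjects (11.2) and two nights each, which gives 25 × 2 = 50 onset pairs if complete.

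**Error model.** Let L ≥ 0 be the latency (true onset minus lights out) and e the device error (device minus true onset). Then

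reported error = device − lights out = e + L.

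**Case 1: the device detects true onset (e = 0).** The true MAE is 0. Reported bias = reported MAE = mean(L), and reported RMSE = √(mean² + SD²).

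| Assumed mean L (min) | Reported bias and MAE | RMSE if SD = mean/2 | RMSE if SD = mean |
|---|---|---|---|
| 5 | 5 | √(25 + 6.25) = 5.6 | 7.1 |
| 15 | 15 | √(225 + 56.25) = 16.8 | 21.2 |
| 30 | 30 | √(900 + 225) = 33.5 | 42.4 |

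**Case 2: the device calls sleep at lights out (e = −L).** The reported error is 0 on every night. The true MAE is mean(L): 5, 15 or 30 minutes.

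**Between the two cases.** At a fixed L, |e + L| > |e| exactly when e > −L/2. Error is overstated above that point and understated below it. With L = 15 minutes:

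| e (min) | True absolute error | Reported absolute error |
|---|---|---|
| −15 | 15 | 0 |
| −7.5 | 7.5 | 7.5 |
| −5 | 5 | 10 |
| 0 | 0 | 15 |
| +10 | 10 | 25 |

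**With random device error.** A simulation used a skewed latency (gamma, shape 2) with mean 5, 10, 20 or 30 minutes and a normal device error with SD 5 minutes. Against lights out, the accurate device reports an MAE of 6.3, 10.6, 20.2 or 30.1 minutes, and the lights-out device reports 4.0 throughout. Against true onset the figures swap: 4.0 for the accurate device and 6.3, 10.6, 20.2 or 30.1 for the other. The worse device ranks as better at every latency tried.

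**Sample size.** Assume mean 15 and SD 7.5 minutes with a perfect device. The apparent bias is 15 minutes. Its 95% half-width is 1.96 × 7.5/√50 = 2.1 minutes if nights are independent, or 1.96 × 7.5/√25 = 2.9 minutes if a subject's two nights are fully correlated. The true bias is 0, so the interval is tight around the wrong value. With the 5 additional subjects and no dropout (60 independent nights), the standard error falls only from 7.5/√50 = 1.06 to 7.5/√60 = 0.97. The bias stays at 15.

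**Wake time.** This part is minor. Staff wake the subject, so the recorded time is off only when the subject was already awake or was slow to get up.

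**The case against.** The strongest reply is that the material for a correction is already being collected. If the recorded times are lights out and arising, lying awake after lights out is a period of wakefulness between them and should be annotated. True onset could then be derived at analysis, possibly by a rule in the SAP, which is not at hand. This is a fair point, and it is what makes the fix cheap. It does not remove the defect. No passage of the protocol moves the onset to the end of the first wake period. No bedside criterion for being asleep is stated, and an SAP finalised before database lock cannot supply one that observers did not apply during the night.

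A second reply is that the sentence describes when staff fill in the form and does not define onset as lights out. That reading fits poorly with the next sentence, which treats the two times as the limits within which wakefulness is noted. If it were right, staff would have no rule for judging onset, and the same edit would be needed.

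Third, the device's onset output is undefined. If it marks the start of time in bed, lights out is the matching reference and only the endpoint's name is wrong. This stands, and renaming is offered below for that reason.

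Some smaller points also stand. The offset vanishes on a night with zero latency. A device triggered by lying down before lights out would still show that interval as error. The separation of sleep from lying appears in section 4.1, but section 11.3 leaves sleep out of the activity classes. The exclusion of "History of sleep disorders or self-reported insomnia or other sleep conditions" makes long latencies less likely. The magnitudes are assumed throughout. Observer-judged onset has its own error, which the documents do not quantify.

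**Conclusion.** The concern holds. As written, the protocol compares the device's sleep onset with lights out and reports the result as accuracy of sleep onset. The bias equals the mean latency for an accurate device, and an error of the same size is hidden for a device that calls sleep at lights out. On assumed mean latencies of 5 to 30 minutes, that is 5 to 30 minutes of MAE in either direction. The direction and the break-even at half the latency follow from the definitions alone. The sizes rest on the assumed latencies.

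The consequence is limited. The analysis is descriptive with no acceptance limit, and onset is part of one of seven endpoint groups. The outcome is a misleading accuracy figure, not a failed test. The point should be fixed before the first subject, because the observer's criterion has to be applied at the bedside.

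**What to change.** In both 8.8.3 and 8.10.1:

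- Record lights out and arising as separate CRF fields, neither labelled as sleep onset or wake time.
- Define reference sleep onset as the end of the observer-annotated wakefulness that follows lights out.
- Define reference wake time as the start of the final annotated wakefulness or, if there is none, the time staff woke the subject.
- State the observer's criterion for sleep and fix it before enrolment. One example is the start of the first run of a set number of consecutive minutes with eyes closed and no purposeful movement.
- Report device onset against lights out as a separate comparison, so that both are visible.

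If the sponsor does not want observer-judged onset, the alternative is to rename the endpoint in 4.1 and 11.3 as time to bed and time out of bed, not to report it as sleep-onset accuracy, and to state that sleep onset is not validated in this study.

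The cost is two CRF fields, one definition and one criterion in two sections, plus observer training. All-night observation and annotation are already planned. The drawback is that judged onset is less crisp than lights out, carries observer error, and does not support reporting to the second.
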